DOR	Duration of response will be calculated as the time from initial response (for any patient with a complete or partial response initially) until the earliest of either disease progression or death. Patients who discontinue therapy due to a reason other than progression will be censored on the date of discontinuation. Patients still on therapy at the time of data cut-off will be censored on their last visit date.
TOT	Time from initiation of a line of therapy until discontinuation for any reason; patients on therapy at the time of data cut-off will be censored on the last date of treatment.
TTP	Time from initiation of a line of therapy until discontinuation due to disease progression; patients on therapy or those who discontinued due to a reason other than disease progression will be censored on the last date of treatment.

PFS	Time from initiation of a line of therapy until disease progression or death; patients on therapy at the time of data cut-off will be censored on the last date of treatment. Patients who discontinue a line of therapy for a reason other than disease progression but who subsequently die prior to the receipt of any other therapy will be considered an event on the date of death.
OS	Time from initiation of any therapy in the metastatic setting until death; patients alive at the time of data cut-off will be censored on the last date the patient was seen by the provider/clinic.
AE	An adverse event is defined as any untoward medical occurrence in a patient administered a medicinal product and which does not necessarily have a causal relationship with this treatment. AEs from a prepopulated list (including “other, please specify”) during each line of therapy will be indicated by providers. The number and proportion of patients experiencing each AE reported during afatinib or other systemic therapy will be reported. See Section 11.1 and Table 3 for further details.

In addition to TOT, to further characterize treatment patterns for those treated with afatinib and those treated with other systemic therapy, the following will be collected (and calculated based on the collected data):

- Treatment history (i.e., regimens, duration, number of cycles, sequence)
- Starting dose of afatinib or other systemic therapy
- Dose modifications of afatinib or other systemic therapy (i.e., dose reductions and their timing, dose increases and their timing, dose delays and their duration and timing)

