- Rationale for afatinib or other systemic therapy discontinuation

AEs will be collected and analyzed in the Clinical Study Report. Providers will be shown information describing what constitutes an AE/ADR/SAE/FAE per BI policies. The processes for safety reporting and analysis of the safety data will be implemented and conducted as per the BI non-interventional study (NIS) standard operating procedures. [REDACTED] will complete any reporting of events to BI per event reporting protocols.

The diagnosis, time, attribution (treatment-related or not per provider interpretation) and severity of the reported AEs during index therapy will be collected. If death is cited as rationale for discontinuation then provider will abstract data related to date of death, cause of death.

Table 3. Adverse events data collection.

Variable	Definition / response options
AEs during a given line of therapy	During each line of therapy, providers will indicate the AE that occurred including severity.
Start date of AE	Date each AE occurred

Severity (see section 11.1)	
Severity of each AE, as assessed by the provider, provided the following guidance:
 
 • Mild (mild symptoms; clinical or diagnostic observations only [e.g. lab work]; intervention not performed) • Moderate (minimal, local or noninvasive intervention performed [e.g., administration of fluids]) • Severe (medically significant ranging from not immediately life-threatening, life-threatening consequences, to death related to AE; [e.g., extensive monitoring, hospitalization or prolongation of hospitalization])
Resolution	
Outcome of each AE will be collected as:
 
 • Recovered/Resolved • Recovered/Resolved with sequelae • Not yet recovered/Not yet resolved • Fatal • Unknown
Outcome	
For all AEs, the outcome of the AE, regardless of severity indicated, will be assessed by participating providers. These outcomes will allow for the classification of serious and fatal AEs as defined in Section 11
 
 • Dose reduction • Dose hold/dose delay/schedule change • Discontinuation of treatment • Unscheduled office visit/treatment • Resulting in death • Life-threatening • Required inpatient hospitalization • Resulted in persistent or significant disability • Prolonged existing hospitalization
End date of AE	Date AE resolved/patient recovered (if resolved/recovered)

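### Table 2 dates TTP at stopping the drug for progression, and its DOR and DOCB censoring sentence conflicts with those rows' own event definition and with the PFS rule for death after a stop

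*Combined protocol and SAP*

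**What the plan says.** All the relevant definitions are in Table 2 of section 9.3.2. Section 9.7 refers back to that table for every outcome calculation and applies Kaplan-Meier to all the time-to-event outcomes.

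- **TTP** is "Time from initiation of a line of therapy until discontinuation due to disease progression". On censoring, "patients on therapy or those who discontinued due to a reason other than disease progression will be censored on the last date of treatment".
- **DOR and DOCB** run from initial response "until the earliest of either disease progression or death". The next sentence in each row is "Patients who discontinue therapy due to a reason other than progression will be censored on the date of discontinuation". Neither row makes an exception for death.
- **PFS** runs from the start of a line of therapy to progression or death. It adds that patients who stop for a reason other than progression and "who subsequently die prior to the receipt of any other therapy will be considered an event on the date of death".

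The text introducing Table 3, on adverse events, bears on the same point: "If death is cited as rationale for discontinuation then provider will abstract data related to date of death, cause of death". The plan thus foresees death as a recorded reason for stopping. Dates of progression and of death are among the data to be collected (sections 9.1 and 9.2).

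**The concern.** TTP as defined is a treatment-duration measure limited to one cause of stopping. It depends on when the provider stopped the drug as well as on when the disease progressed. DOR and DOCB promise one event and then apply a censoring rule that removes part of it, and that rule treats death after a stop differently from PFS.

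DOR is in objective 2 and TTP in objective 3, and section 9.1 lists DOCB. The rationale says the results may be used in label-expansion applications. The study is descriptive and tests no hypothesis, so no error rate is at stake. What is at stake is whether the reported medians mean what their names say, and whether two programmers following Table 2 would produce the same dataset.

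**Working it through.** The plan gives no median, event count or rate that depends on these definitions, so there is no figure to reproduce. The main check is to apply each row to the same patients. The last column applies to patients who entered DOR or DOCB through their initial response.

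| Patient | PFS | TTP | DOR and DOCB |
|---|---|---|---|
| A. Progresses; drug stopped later for progression | Event at progression | Event at the later stop | Event at progression |
| B. Progresses; still on drug at cut-off | Event by the definition, although the on-therapy censoring clause has no exception | Censored at last treatment | Event by the definition, with the same missing exception |
| C. Stops for toxicity; dies before other therapy | Event at death, explicitly | Censored (conventional for death) | Censored at the stop |
| D. Stops for toxicity; progresses before other therapy | Event by the general definition; not stated for this case | Censored at last treatment | Censored at the stop |
| E. Dies on treatment without progression | Event | Censored (conventional) | Event by the first sentence; censored by the second if death is the reason for stopping |

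Rows A and B show the TTP problem, row C the conflict with PFS, and row E the contradiction inside the DOR and DOCB rows.

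**Size of censoring at non-progression stops (all inputs assumed).** Let the on-treatment event hazard be h = ln 2 / 6 = 0.1155 per month (median 6.0). Let a share s stop first for another reason, so that the stopping hazard is k = h·s/(1 − s). Let the hazard after the stop be r·h. Kaplan-Meier under the current rule estimates exp(−ht), with median 6.0 whatever r is. With all later events counted,

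S(t) = exp(−(h+k)t) + [k/(h+k−rh)]·[exp(−rht) − exp(−(h+k)t)].

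For s = 0.30, k = 0.1155 × 0.30/0.70 = 0.0495. Solving S(t) = 0.5:

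- r = 0.5: median 6.53; the current rule is off by 6.0 − 6.53 = −0.5 months
- r = 1: median 6.0; difference 0
- r = 2: median 5.44; difference +0.6
- r = 3: median 5.13; difference +0.9

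At s = 0.10 the differences run from −0.1 (r = 0.5) to +0.3 (r = 3). Simulations of 400,000 patients per scenario, with administrative censoring uniform on 6 to 45 months, give the same medians.

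**Effect of the fix.** In the same simulations at s = 0.30, half or all of those who stop start new therapy 0.5 to 3 months later and are censored then. The median becomes 5.25 to 5.39 at r = 3 (5.1 with full follow-up) and 6.23 to 6.39 at r = 0.5 (6.5 with full follow-up). The remaining error is about 0.1 to 0.3 months in either direction. At r = 1, events per 70 patients rise from 46.1 to between 49.7 and 56.0.

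**TTP lateness.** If 30% of patients stay on drug for a mean of 1 or 2 months past progression, a median of 6.0 becomes 6.3 or 6.7. A harsher set of assumptions (median 8 months, every drug stop 1.5 months after progression, post-stop hazard 1 or 2 times the on-treatment hazard) gives 0.9 to 1.8 months. The gap between the two results comes from the assumptions alone.

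**Scale.** The 95% sampling range of a 6-month median at s = 0.30 is about 4.1 to 8.7 months with 70 patients. With 21 responders (an assumed 30% ORR, 0.30 × 70) it is roughly 3 to 12.

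**The case against.** The best defence is that Table 2 describes a family of on-treatment measures: TOT is stopping for any reason, and TTP is stopping for progression. PFS and OS are reported beside them and count deaths, and the rules are stated openly. On-treatment censoring of DOR can be a deliberate choice. This has force, but the plan does not state it as a choice. It would not explain an outcome named time to progression that is not dated at progression, nor resolve the two adjacent DOR sentences.

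Several stronger readings are tempting and do not hold:

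- **On-treatment deaths will be censored.** A reader might infer this, and under exponential times it would move a 6.0-month median to 6/(1 − d): 6.3 at d = 5% of events and 7.5 at d = 20%. But the reading leaves death almost no role in the row's own event definition, and the sentence on death as a reason for stopping concerns data collection. The text supports a contradiction that needs resolving, not a certain consequence.
- **These outcomes drop every event that PFS counts.** PFS explicitly counts only death after a non-progression stop and is silent on progression after one. Leaving deaths out of TTP is conventional.
- **The medians are biased upward.** The sign of the stop-censoring effect depends on r, and the documents give no information about r.
- **All four outcomes need one censoring date.** On-therapy patients are censored at last visit for DOR and DOCB ("Patients still on therapy at the time of data cut-off will be censored on their last visit date") but at last treatment for PFS ("patients on therapy at the time of data cut-off will be censored on the last date of treatment"). This is a matter of preference, and last visit can credit progression-free time that nobody assessed.

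**Conclusion.** The point holds as a fault of definition. TTP is dated at the wrong event for its name. The DOR and DOCB censoring sentence conflicts with the event in the same rows and with the PFS treatment of death after a stop. Nothing in section 9.7 or elsewhere in the plan reconciles them. These conclusions rest on the text and need no assumption.

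The numerical consequence is uncertain. From about −0.5 to +0.9 months on a 6-month median is an illustration over assumed stopping shares of 10 to 30% and post-stop hazard ratios of 0.5 to 3, and it lies within sampling error at 70 patients. The study should correct this before analysis, but the point does not undermine PFS or OS. The PFS row also gives no censoring date for a patient who is off therapy, alive and progression-free; that is a clarification only.

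**What to change.** 1. **TTP:** define it as start of the line of therapy to documented progression before new systemic therapy, with death without progression censored. If the present quantity is kept, report it as time to discontinuation for progression.
2. **DOR and DOCB:** state that on-treatment death is an event. After a non-progression stop and before new systemic therapy, count death, as PFS does, and documented progression where it is captured.
3. **Sensitivity:** keep the current on-treatment-censored DOR and DOCB as labelled sensitivity analyses.
4. **Clarification:** give PFS a censoring date for patients off therapy, alive and progression-free.

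The cost is rewording in Table 2, matching code and one eCRF check. Progression and death dates are already planned, and abstraction runs to last follow-up or death (section 9.4). However, the plan does not say that progression after a non-progression stop is captured. That should be checked before the pre-test, because eCRF changes arising from the pre-test go back to the IRB (section 9.8.1).

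Two downsides remain. Progression after a stop may be under-documented; section 9.9 already warns that outcomes after the last visit may be missing. Censoring at new therapy may also still be informative.

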The ORR among patients with *NRG1* gene fusion-positive solid tumors treated with afatinib and among patients with *NRG1* gene fusion-positive solid tumors treated with other systemic therapy will be calculated as the proportion of patients with a complete response (CR) or partial response (PR) out of all patients (CR+PR/all patients) (see **Table 2** below). Disease response for determining the ORR will be reported as recorded in the patient's EHR, including the date of radiographic imaging used to substantiate the patient's initial and best response to therapy. Providers will indicate whether the patient experienced a CR, PR, stable disease (SD), or progressive disease (PD). No independent blinded review of radiology studies will be conducted. Lesion measurements at baseline (initiation of afatinib; initiation of other systemic therapy for non-afatinib treated patients), initial response, and best response will be abstracted as available. Changes in the number, locations, and sizes of lesions at initial and best response to therapy will be evaluated by [REDACTED] using RECIST v1.1 guidelines. The sum of lesion measurements will be assessed at baseline and at follow-up scans to calculate the percent change in sum of target lesions, as well as account for new lesions on follow-up scan in order to classify response by RECIST v1.1 criteria. Actual scan images will not be reviewed; the calculation of real-world disease response will be based on the lesion measurements provided. Other outcomes include PFS, TOT, TTP, OS, DOR, DOCB, AEs. Definitions of these outcomes are shown in **Table 2**.

Table 2. Study outcomes and definitions.

Outcome	Definition
ORR	Proportion of patients with a complete response (CR) or partial response (PR) out of all patients (CR+PR/all patients) at initial response assessment and best response
DOCB	Duration of clinical benefit (DOCB) will be calculated as the time from initial response (for any patient with a complete, partial, or stable disease response initially) until the earliest of either disease progression or death. Patients who discontinue therapy due to a reason other than progression will be censored on the date of discontinuation. Patients still on therapy at the time of data cut-off will be censored on their last visit date.

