Random data validation occurs by selecting a random eCRF from each provider submitting a patient. Providers who have been previously verified by [REDACTED] will not be subject to completion of the random validation. A verified provider is any physician abstractor who has completed at least two of the following: (1) completed and acknowledged our web-based chart data abstraction training in the past 2 years, (2) participated in a chart review pre-test with screen sharing, (3) participated in 2 previous chart review studies in the past 2 years and accurately validated data, and (4) have completed a phone interview with the [REDACTED] team for data validation. A provider may be verified but still required to answer questions regarding patients with data flagged by [REDACTED] or [REDACTED] groups. Providers subject to random validation are asked to complete a 3-data point validation exercise for the patient whereby the provider is given the unique patient identifier but no other information. The provider is asked to re-enter the respective data elements. The three data points may include elements such as the month/year of index treatment initiation, stage at diagnosis, and date of index treatment discontinuation (or date of last treatment/prescription if patient is still on therapy). A provider who fails to validate all data points for a selected patient will be required to submit to further clinical data review. Patients for whom the data are deemed questionable by the research team staff will be excluded; providers will not be compensated for excluded data. No resampling to replace the excluded eCRF will occur. Provider who are nonresponsive to any validation request will have all data submitted excluded from the study.

For all data validation processes, a log of records that undergo statistical and clinical review will be kept, recording the reason a given record was flagged for further follow-up. Should data quality checks and confirmation with providers reveal discrepancies, corrections will be made to the database. These corrections (including whether a record was dropped entirely) will be documented in an audit trail. The number of records undergoing each step of data validation and the number of records corrected or excluded from the final data set will be reported.

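### For patients still on therapy, PFS is censored at last treatment but DOR and DOCB at last visit, so follow-up for the same event can end on two dates

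*Combined protocol and SAP*

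**What the plan says.** All censoring rules are in Table 2 of Section 9.3.2. For a patient still on therapy at data cut-off they read as follows.

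- **PFS** runs "until disease progression or death; patients on therapy at the time of data cut-off will be censored on the last date of treatment".
- **DOR** runs, "for any patient with a complete or partial response initially) until the earliest of either disease progression or death". For ongoing patients: "Patients still on therapy at the time of data cut-off will be censored on their last visit date".
- **DOCB** has the same event and the same last-visit rule as DOR. It also admits patients whose initial response was stable disease.
- **TTP** has a different event: "Time from initiation of a line of therapy until discontinuation due to disease progression". Its censoring rule is: "patients on therapy or those who discontinued due to a reason other than disease progression will be censored on the last date of treatment".
- **TOT** ends at discontinuation for any reason and is also censored at last treatment.

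Section 9.7 applies Kaplan-Meier to all of these outcomes and refers back to Table 2 for the definitions. Annex 1 lists no stand-alone document that could hold a further rule. On assessments, Section 9.3.2 collects response as charted, "including the date of radiographic imaging used to substantiate the" initial and best response. Lesion measurements at baseline, "initial response, and best response will be abstracted as available". Section 9.2 says that progression dates are collected. No date of last progression-free assessment is named.

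**The concern.** PFS, DOR and DOCB watch for the same event in the same patient, so for an ongoing responder all three should stop on the same calendar date. Under Table 2 they need not. If the last treatment precedes the last visit, time to response plus DOR exceeds PFS in a patient who has had no event. If it follows the last visit, PFS claims event-free time that DOR does not. Table 2 also does not require that either date be one on which the patient was found free of progression.

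This matters because PFS and DOR are stated objectives (Section 8) and the results may support label-expansion applications (Section 7). Treatment starts are allowed up to 31 March 2020 and minimum follow-up is about 3 months (Section 9.1), so some patients will probably still be on therapy.

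**Working it through.** The plan states no figure that depends on the censoring rule, so there is nothing to reproduce. The check has two parts: a set of dates for one patient, and an illustration of size.

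**1. One ongoing responder.** Assumed days from treatment start: response 60, last scan 120, last visit 150, no progression. DOR is censored at 150 − 60 = 90 days, so its clock stops on day 150. PFS is censored on the last treatment day.

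| Last treatment (day) | PFS clock stops | DOR clock stops | DOR end − PFS end |
|---|---|---|---|
| 120 | 120 | 150 | +30 |
| 135 | 135 | 150 | +15 |
| 150 | 150 | 150 | 0 |
| 165 | 165 | 150 | −15 |

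The dates can differ in either direction, and they agree when the last treatment falls on the last visit. If both are censored at the last scan, both clocks stop on day 120: PFS is 120 days and DOR is 120 − 60 = 60 days.

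**2. Effect on the Kaplan-Meier median.** Every input here is an assumption.

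- Latent progression time T is exponential with rate ln 2 / median; a month is 30.44 days.
- Scan intervals are uniform between 0.6 and 1.4 times the nominal interval. An event is dated at the first scan at or after T.
- Cut-off C is uniform from 90 to 1280 days.
- Last visit is 28 × floor(C/28), or the last scan if later. Last treatment is C.
- There are 200,000 patients per scenario. S(t) = ∏(1 − dᵢ/nᵢ), and the median is the first t with S(t) ≤ 0.5.

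Median PFS in months, by censoring date:

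| True median, scan interval | Scan | Visit | Treatment | Treatment − visit | Treatment − scan |
|---|---|---|---|---|---|
| 4, 8 wk | 4.89 | 4.94 | 4.97 | 0.03 | 0.08 |
| 4, 12 wk | 5.50 | 5.58 | 5.60 | 0.02 | 0.10 |
| 4, 16 wk | 5.62 | 5.92 | 6.01 | 0.09 | 0.39 |
| 6, 8 wk | 6.88 | 6.95 | 7.00 | 0.05 | 0.12 |
| 6, 12 wk | 7.24 | 7.40 | 7.46 | 0.06 | 0.22 |
| 6, 16 wk | 7.80 | 7.99 | 8.04 | 0.05 | 0.24 |
| 12, 8 wk | 12.70 | 12.88 | 12.98 | 0.10 | 0.28 |
| 12, 12 wk | 13.01 | 13.37 | 13.52 | 0.15 | 0.51 |
| 12, 16 wk | 13.35 | 13.88 | 14.03 | 0.15 | 0.68 |

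A rerun with the longest follow-up cut to 39 months, as in Section 9.1 (39 × 30.44 = 1187 days), gave 0.02 to 0.17 and 0.08 to 0.74 month for the last two columns. With perfectly regular scans on a common grid, all three rules gave the same curve. Other assumed patterns with long follow-up gave 0.00 to 0.04 month for treatment versus visit, and 0.03 to 0.25 month for cut-off versus last scan. The figures are orders of magnitude, not predictions.

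**The case against.** The strongest reply is that this hardly changes any estimate. That stands. The treatment-versus-visit shift is small beside sampling error: with 70 patients and a true median of 5.5 months, a simulated 95% range for the median was about 5.1 to 8.6 months.

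A second reply is that the last scan is not clearly the less biased date. When events are dated at the detecting scan and cut-off is independent, Kaplan-Meier with censoring at cut-off is valid for detected PFS. In a simulation with a true median of 5.5 months and cut-off uniform on either 3 to 20 or 3 to 42 months, the cut-off rule gave stable medians across the two follow-up patterns (6.60 and 6.65 with 2-month scans). The last-scan rule moved more (6.32 and 6.53). This stands too. The case for an assessment date is that it is documented and common to all three endpoints, not that it removes bias. PFS progression is not restricted to imaging, so a visit may itself be a clinical assessment.

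A reader might go further in three ways that the documents do not support.

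- **TTP belongs in the same complaint.** Its event is a treatment stop, so last-treatment censoring fits it. A scan date would create a new mismatch.
- **The rule biases the cohorts differently, oral drug against infusion.** Section 9.8.2 does mention "or date of last treatment/prescription if patient is still on therapy", but as an example of a validation item, not as the PFS definition. Other systemic therapy is not limited to infusions, the afatinib cohort is not limited to monotherapy (Section 9.3.1), and no comparison between cohorts is planned.
- **Analysts could not repair this later.** The eCRF itself is not in the documents. Section 9.3.2 refers to follow-up scans and Section 9.8.2 to radiology results in submitted forms. All that can be said is that a last-assessment date is not named.

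**Conclusion.** The point holds for PFS against DOR and DOCB in patients still on therapy. Table 2 gives two end dates for follow-up of one event, ties neither to a disease assessment, and gives no reason for the difference. This follows from the text and needs no assumption.

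The numerical effect is small. Treatment date versus visit date is worth about 0.05 month in median PFS at a true median of 6 months, and 0.02 to 0.15 month over the scenarios tabulated. Last scan versus last treatment is worth about 0.1 to 0.25 month at that median, and reaches 0.68 month only with a 12-month median and 16-week scans. These sizes depend on the assumed scan and visit patterns and on last treatment falling at cut-off; a last treatment before the last visit would reverse the sign of the first contrast. The reason to act is that the definitions should be coherent and can be aligned cheaply before data collection, not that the reported medians would be materially wrong.

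**What to change.** In Table 2, give PFS, DOR and DOCB one censoring date for patients still on therapy at cut-off. The preferred date is the last assessment, imaging or clinical, documented as free of progression. Add that date to the eCRF before launch and report last-visit censoring as a sensitivity analysis. At minimum, and with no new field, change the PFS rule to the last visit date already used for DOR and DOCB. Keep the last treatment date for TOT and TTP.

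The cost is a wording change and one eCRF field, which can go through the pre-test and IRB filing already planned in Sections 9.8.1 and 9.8.2. Medians may fall slightly under the preferred rule.
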